## **2.4 Patient disposition, demographics and other baseline characteristics**

Demographic and baseline characteristics will be summarized and listed based on the Randomized Analysis Set. The following background and demographic variables will be analyzed:

**Continuous variables:**

- Age
- Height
- Weight
- Body mass index (BMI)

**Categorical variables:**

- Age categories (<20, [20, 30), [30, 50),  $\geq$ 50)
- Age categories (<30, [30, 40), [40, 65),  $\geq$ 65)
- Gender
- Weight categories (<70 kg, [70 kg, 90 kg),  $\geq$  90kg)
- Weight categories (<90 kg,  $\geq$  90kg)
- Race
  - White
  - Black or African American
  - Asian
  - Native Hawaiian or Other Pacific Islander
  - American Indian or Alaska Native
- Ethnicity
  - Hispanic or Latino
  - Not Hispanic or Latino
  - Not reported
  - Unknown
- Smoking status at baseline
- Region
- Current antibiotic use (Yes/No)

Hidradenitis suppurativa specific baseline characteristics and history of disease will be summarized:

**Continuous variables:**

- Baseline AN count
- Baseline inflammatory nodule count
- Baseline abscess count
- Baseline draining fistula count
- Baseline total fistulae count
- Baseline NRS
- Baseline Hidradenitis Suppurativa Physician's Global Assessment (HS-PGA)
- Baseline modified Hidradenitis Suppurativa Score (mHSS)
- Baseline hsCRPBsl ESR

- Dermatology Life Quality Index (DLQI) total score
- EuroQol-5 Dimension (EQ5D)
- Time since diagnosis of HS
- Time since HS symptom(s) onset

**Categorical variables:**

- Baseline Hurley stage
- Prior surgery for HS
- Family history of HS
- Previous exposure to systemic biologic therapy
- Previous exposure to adalimumab
- Previous exposure to systemic antibiotics
- Previous exposure to non- biologic and non-antibiotic systemic therapy

*Body Mass Index (BMI)* will be calculated using the following formula:

$$\text{BMI} = (\text{body weight in kilograms}) / (\text{height in meters})^2$$

For BMI, height and body weight of the last value prior to first dose will be used as a baseline value. If there is no weight or height recorded prior to taking the study treatment, BMI will be missing.

Time since diagnosis of hidradenitis suppurativa will be calculated using the following formula:

$$\text{Time since diagnosis} = (\text{inform consent date} - \text{first diagnosis date} + 1) / 365.25$$

Time since disease duration (defined as onset of symptom) will be calculated using the following formula:

$$\text{Time since onset} = (\text{inform consent date} - \text{Symptom(s) onset date} + 1) / 365.25$$

The first diagnosis date of hidradenitis suppurativa and hidradenitis suppurativa symptom(s) onset will be imputed according to the imputation rules in [Section 5.1.4](#).

Unless otherwise specified, summary statistics will be presented for continuous variables for each treatment group in the randomized set. The number and percentage of subjects in each category will be presented for categorical variables for each treatment group in the randomized set.

Any condition entered on the Relevant medical history / current medical conditions CRF will be coded using the MedDRA dictionary. They will be summarized by System Organ Class (SOC) and Preferred Term (PT) of the MedDRA dictionary.

**Patient disposition**

The number and percentage of subjects in the Randomized Analysis Set who completed the entire treatment period and who discontinued the treatment prematurely (including the reason for discontinuation) will be presented for each treatment group. A listing will be also provided, and detail reason for discontinuation might be displayed if applicable.

For each protocol deviation, the number and percentage of subjects for whom the deviation applies will be tabulated. All protocol deviations will be presented by PD category as well as by PD sub category (PD short description).

## **2.5 Treatments (study treatment, rescue medication, concomitant therapies, compliance)**

### **2.5.1 Study treatment / compliance**

The analysis of study treatment data will be based on the Safety Set.

The number of secukinumab and placebo doses will be summarized by treatment group by means of contingency tables.

The duration of exposure to study treatment will be summarized by treatment group. In addition, the number of subjects with exposure of at least certain period of time will be displayed using the following categories: “any exposure”, “ $\geq 1$  week”, “ $\geq 2$  week”, “ $\geq 3$  week”, “ $\geq 4$  weeks”, “ $\geq 8$  weeks”, “ $\geq 12$  weeks”, “ $\geq 16$  weeks”, “ $\geq 24$  weeks”, “ $\geq 32$  weeks”, “ $\geq 40$  weeks” and “ $\geq 52$  weeks”.

Duration of exposure will be defined as the time from first dose of study medication to the last dose plus 84 days or last visit (including follow-up visits) whichever occurs earlier, i.e., for subjects who discontinued or have their last visit earlier than 84 days, the end of study treatment exposure will be the date of the last study visit in the follow-up period or in the corresponding treatment period.

$$\text{Duration of exposure (days)} = \min(\text{end date, last dose date} + 84) - \text{first dose date} + 1$$

$$\text{Duration of exposure (years)} = \text{duration of exposure (days)} / 365.25$$

$$\text{Duration of exposure (100 subject years)} = \text{duration of exposure (years)} / 100$$

#### **2.5.1.1 Visit windows**

Visit windows will be used for the data that is summarized by visit. They are based on the study evaluation schedule and comprise a set of days around the nominal visit day. For any assessment, there are the protocol defined scheduled visits around which visit windows were created to cover the complete range of days within the study. For subjects randomized to Placebo to secukinumab 300 mg every 2 weeks arm and Placebo to secukinumab 300 mg every 4 weeks arm, the day of taking the first secukinumab dose will also need to be taken into visit window consideration. Further information will be found in Study Programming Dataset Specifications (PDS). The visit windows are shown in [Table 2-1](#). In these tables, the days are counted since the first dose of study treatment (study day 1). These visit windows apply to measurements taken at every visit. For assessments collected less often different visit windows will be applied as detailed below.

When visit windows are used, all visits will be re-aligned, i.e. they will be mapped into one of the visit windows. E.g., if the Week 4 visit of a subject is delayed and occurs on Day 60 instead of on Day 29, it will be re-aligned to visit window Week 8. In the case of major deviations from the visit schedule, or due to unscheduled visits, several assessments of a subject may fall in a

particular visit window (either scheduled or unscheduled). Statistical approaches to handle multiple assessments in a given visit window are specified below.

**Table 2-1 Assessment windows for scheduled visits for analyses based on the entire study period**

Analysis Visit	Week	Scheduled Day	Visit Window
Baseline	BSL	1	-28 days to Day 1*
Week 1	1	8	Day 2-11
Week 2	2	15	Day 12-18
Week 3	3	22	Day 19-25
Week 4	4	29	Day 26-43
Week 8	8	57	Day 44-71
Week 12	12	85	Day 72-99
Week 16	16	113	Day 100-120
Week 18	18	127	Day 121-134
Week 20	20	141	Day 135-155
Week 24	24	169	Day 156-183
Week 28	28	197	Day 184-211
Week 32	32	225	Day 212-239
Week 36	36	253	Day 240-267
Week 40	40	281	Day 268-295
Week 44	44	309	Day 296-323
Week 48	48	337	Day 324-351
Week 52	52	365	Day 352-379
Follow up	60	421	Starting from day 380

\* Baseline measurement before the first drug administration.

For HiSCR, HiSCR components inflammatory nodules, abscesses, draining fistulae, Flare and other lesion related assessments, Screening 1 visit, Screening 2 visit and baseline visit will be adjusted per below table

Analysis Visit	Week	Scheduled Day	Visit Window
Screening 1	-4	-21	-28 days to -14 days
Screening 2	-2	-7	-13 days to -1 days
Baseline	BSL	1	Day 1

For parameters which are not collected at every visit (e.g. weight, laboratory parameters, DLQI), visit windows defined in and [Table 2-1](#) will be combined. The following rules are used to determine the visit window for an applicable visit post baseline: “Lower limit” = “upper limit of prior applicable visit” + 1. “Upper limit” = “target day of current visit” + integer part of (“target day of next applicable visit” – “target day of current visit”)/2. For example, if a parameter is measured at Baseline, Week 12 and Week 28 only, Week 12 visit window will extend from Day 2 to Day 141 (combining Week 1 to Week 20 visit windows), Week 28 will extend from Day 142 to Day 379 (combining Week 24 to Week 52). If more than one assessment falls into the interval, the rules defined below are applied.

The analysis visit will be used for listing of visit and period for both safety and efficacy data. If a visit falls after the last visit window (after Day 379) it is not assigned to an analysis visit and will be listed under label “After Week 52”.

In case patients make use of the additional unscheduled visits for assessments other than the PGA of skin pain (NRS) before the Week 52 assessment (which were introduced due to the pandemic; see [Section 1.1](#)), the visit window for Week 52 and the follow-up period does not apply to these patients. The actual Week 52 visit will be taken for these patients as long as the time difference between this assessment and the last dosing is at most 4 weeks. The actual follow-up visit will be taken for these patients as long as the time difference between this assessment and the last dosing is at most 12 weeks.

For analysis of HS Symptom Diary assessment, Patient’s Global assessment of skin Pain, the weekly average HS Symptom component score and NRS from Baseline to Week 52 is calculated based on the 7 available daily scores: Baseline (Week 0) will be average of HS symptom Diary score from day -7 to day -1, Week 1 will be average of score from day 1 to day 7, Week 2 will be average of score from day 8 to day 14 and so on. For any week with less than 4 diary entries within the week, the weekly average component score will be recorded as missing.

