Days	-28 to -14	-13 to -1	1	8	15	22	29	57	85	113	120	127	134	141	169	197	225	253	281	309	337		365	421	
Lesion count (physician)	X	X	X		X		X	X	X	X		X		X	X	X	X	X	X	X	X		X	X	
Flare assessment ⁴	X	X	X		X		X	X	X	X		X		X	X	X	X	X	X	X	X		X	X	
Numerical Rating Scale for pain assessment ⁵	Completed daily in the eDiary										Completed weekly in the eDiary														
Modified Hidradenitis Suppurativa Score (mHSS)			X							X	X													X	
HS-Physician's Global Assessment				X		X		X	X	X	X						X							X	
Patient's Lesion Count	Completed weekly in the eDiary																								
DLQI				X		X		X		X								X						X	
EQ5D				X		X		X		X								X						X	
Patient Global Impression of severity (PGI-s)			X		X		X		X	X							X							X	
Patient Global Impression of change (PGI-c)			X		X		X		X	X							X							X	
Work productivity Activity Impairment (WPAI)			X		X						X						X			X				X	
HS Symptom Diary ⁶	Completed daily in the eDiary																			X				X	
Hematology	X		X		X		X	X	X	X		X		X		X		X		X			X		
Clinical Chemistry	X		X		X		X	X	X	X		X		X		X		X		X			X		

Period	Screening		Treatment Period 1							Treatment Period 2										Post-Treatment Follow-Up				
	Screening 1	Screening 2	Baseline	Week 1	Week 2	Week 3	Week 4	Week 8	Week 12	Week 16 / EOT1	Week 17	Week 18	Week 19	Week 20	Week 24	Week 28	Week 32	Week 36	Week 40	Week 44	Week 48	UNS 1 to 3	Week 52 / EOT2	
Visit Name																								Week 60 / F8
Days	-28 to -14	-13 to -1	1	8	15	22	29	57	85	113	120	127	134	141	169	197	225	253	281	309	337		365	421

^x Assessment to be recorded in the clinical database or received electronically from a vendor

^s Assessment to be recorded in the source documentation only

¹ These assessments are source documentation only and will not be entered into the eCRF. However, data regarding to which inclusion/exclusion criteria are not met are captured on the Inclusion/Exclusion eCRF.

² While all concomitant medications are recorded on eCRF, patients will record their daily analgesics use on eDiary.

³ AEs /SAEs occurring after the patient has provided informed consent must be reported.

⁴ Occurrence of flare will be calculated from lesion count assessment and does not require any additional action from the site staff.

⁵ Subjects will complete the NRS skin pain assessment using eDiary. From Screening through Week 16, subjects will complete a daily diary of their skin pain. From Week 16 through Week 52, subjects will complete skin pain assessments on a weekly basis.

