12.5 Analysis of secondary endpoints

12.5.1 Efficacy and/or Pharmacodynamic endpoint(s)

The secondary endpoints of this study are planned as follow:

- Percentage change from baseline in AN count at Week 16
- Flare over 16 weeks: Patients who experience at least one flare over 16 weeks. Flare is defined as an at least a 25% increase in AN counts with a minimum increase of 2 AN relative to baseline.
- Pain/NSR30 at Week 16: Patients achieving NRS30 at Week 16, among patients with baseline NRS \geq 3. NRS30 is defined as at least 30% reduction and at least 2 unit reduction from baseline in Patient's Global Assessment of Skin Pain. NRS from baseline to Week 16 is the weekly average score calculated based on the 7 available daily scores: Baseline (Week 0) will be average of NRS score from day -7 to day -1, week 1 will be average of

score from day 1 to day 7, week 2 will be average of score from day 8 to day 14 and so on. For any week with less than 4 diary entries within the week, the weekly average will be recorded as missing.

For the secondary endpoint of percentage change in AN count from baseline to Week 16, an analysis of covariance (ANCOVA) model will be fitted to estimate the treatment differences between the two secukinumab regimens and placebo with treatment group, baseline AN count, Hurley stage, use of antibiotic, geographical region and baseline body weight as covariates.

The analysis method for both flare up to Week 16 and Pain/NRS30 at Week 16 will be the logistic regression: with treatment group, Hurley stage, geographical region, use of antibiotic, baseline body weight and baseline AN counts as explanatory variables for flare endpoints; and with treatment group, Hurley stage, region, use of antibiotic, baseline body weight and baseline NRS as explanatory variables for pain endpoints. Odds ratios will be computed for comparisons of secukinumab dose regimens versus placebo utilizing the logistic regression model fitted. In case of response rates of 0% or of 100% in one of the treatment groups, Fisher's exact test will be applied. Risk difference and confidence intervals for risk difference will be provided.

Testing strategy

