### 2.5.1.2 Multiple assessments within visit windows

When there are multiple assessments in a particular visit window, the following rules are applied to select one value “representing” the subject in summary statistics in a visit window (see [Table 2-2](#)).

For baseline assessment definition see [Section 2.1.2](#). For post-baseline visit windows the following applies (unless otherwise specified):

- for *quantitative variables*, the *closest* to the scheduled day is chosen (if two assessments have the same distance, then the earlier one will be chosen);
- for *qualitative variables*, the *worst* record is selected. It is noted that in the analyses performed, *worst* case is always well defined (e.g., for urine protein values “+” and “++”, the worst case is defined as “++”),
- in case qualitative variables are based on quantitative variables, e.g. DLQI response, the visit will be assigned to the quantitative variable, and this visit will be used for the derived qualitative variable.

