**Table 2-2 Rules for selecting values for analysis within a given visit window**

Timing of measurement	Type of data	Rule
Baseline	All data	See Section 2.1.2
Post-baseline efficacy	All data except for PRO e.g., HiSCR, HS-PGA	The measurement closest to the scheduled day will be used. In the event two measurements are taken equally apart (e.g., 1 day before target date and 1 day after), the earlier one will be used.
Post-baseline efficacy	PRO data	The measurement closest to the scheduled day will be used. In the event two measurements are taken equally apart (e.g., 1 day before target date and 1 day after), the earlier one will be used. For e-diary data, a cut-off at 3:00 PM is used to define the start of a new day. Anything entered before that time (no later than 2:59 PM) refers to the day before. If more than one measurement is taken on the same day (before the cut-off), the latest one will be used.
Post-baseline safety	Summary visit information (e.g. laboratory values, vital signs, etc.)	The (non-missing) measurement closest to the scheduled day will be used. In the event two measurements are taken equally apart (e.g., 1 day before target date and 1 day after), the earlier one will be used.
Post-baseline safety	Notable abnormalities (e.g. vitals signs) and CTCAE grades for laboratory values	The most extreme measurement in the window will be used. Note this means a subject can have a notably high and notably low measurement within an analysis period.

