### **HS Symptom Diary**

For analysis of HS Symptom Diary, the weekly average HS Symptom component score from baseline to Week 52 is calculated based on the 7 available daily scores: Baseline (Week 0) will be average of HS symptom Diary score from day -7 to day -1, Week 1 will be average of score from day 1 to day 7, Week 2 will be average of score from day 8 to day 14 and so on. For any week with less than 4 diary entries within the week, the weekly average component score will be recorded as missing. HS symptom Diary questions will be collected at specific visits only after Week 16 per pre-defined assessment schedule, thus HS Symptom component score after Week 16 is not provided as a weekly average but as single values. Statistics will be provided for absolute and percentage change from baseline of HS symptom component scores by visit up to Week 52 for each treatment group.

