### **Additional endpoints**

Patient's Global Assessment of Skin Pain - at worst will be summarised on the original scale.

The analysis results on Patient assessed lesion count will be reported separately.

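### SAP 2.5.1.1 averages seven daily pain scores through Week 52, but pain is recorded only weekly after Week 16, so later NRS and NRS30 values are missing or undefined

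*SAP*

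**What the plan says.** SAP 2.5.1.1 (Visit windows) treats the HS Symptom Diary and skin pain together: "the weekly average HS Symptom component score and NRS from Baseline to Week 52 is calculated based on the 7 available daily scores". It then adds: "For any week with less than 4 diary entries within the week, the weekly average component score will be recorded as missing".

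Protocol Table 8-1, footnote 5, sets the collection schedule. Pain is a daily diary item from Screening through Week 16. After that, "From Week 16 through Week 52, subjects will complete skin pain assessments on a weekly basis".

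Protocol 12.5.1 has almost the same averaging rule but with a narrower span: "NRS from baseline to Week 16 is the weekly average score calculated based on the 7 available daily scores". It applies the four-entry minimum to NRS within that span.

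For the HS Symptom Diary, SAP 2.11 recognises that collection becomes sparser after Week 16 and makes an exception: "thus HS Symptom component score after Week 16 is not provided as a weekly average but as single values". The SAP has no matching sentence for pain. Under Additional endpoints, SAP 2.11 says only that the Patient's "Global Assessment of Skin Pain - at worst will be summarised on the original scale".

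SAP 2.13 plans NRS30 responder rates by visit to Week 52, figures with confidence intervals, and a mixed effects logistic regression on the time windows from Week 2 to Week 52, per study and pooled. Table 2-7 specifies observed data only for these analyses.

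**The concern.** The derivation rule needs seven scores a week, with at least four present, during a period when the protocol collects one. The SAP took a rule that the protocol confines to Week 16 and extended it to Week 52 without adjusting it to the collection schedule. SAP Section 4, which lists departures from the protocol, mentions only the HS-PGA definition.

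Skin pain up to 52 weeks is a stated exploratory objective. If the rule is followed, the NRS and NRS30 outputs stop at Week 16 although weekly scores are in the database. If programmers use the weekly score instead, they depart from the SAP without a documented rule. SAP 1.1 allows biostatisticians and programmers involved in the primary endpoint analysis to see unblinded Week 16 results, so the rule should be written down beforehand.

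**Working it through.** The plan states no figure on this point, so the check is a count.

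**Inputs**
- Week scheme (SAP 2.5.1.1): Week 1 is Days 1–7, Week 2 is Days 8–14, and so on. Week k is Days 7(k−1)+1 to 7k.
- Planned entries (Protocol Table 8-1, footnote 5): 7 per week through Week 16, then 1 per week.
- Minimum (SAP 2.5.1.1): 4 entries per week.
- Analysis windows (SAP Table 2-1), Week 2 to Week 52: 2, 3, 4, 8, 12, 16, 18, 20, 24, 28, 32, 36, 40, 44, 48, 52, which is 16 windows.

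**Week 16.** Days 7×15+1 = 106 to 7×16 = 112. This ends before the scheduled Week 16 visit on Day 113 and lies within daily collection. There are 7 planned entries, so the mean can be computed.

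**Weeks 17–52.** That is 52−16 = 36 weeks with 1 planned entry each. Since 1 < 4, every one is missing if the minimum covers NRS.

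**By Table 2-1 window.** The windows after Week 16 are 18, 20, 24, 28, 32, 36, 40, 44, 48 and 52, which is 10. The share without a value is 10/16 = 62.5%.

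**By week, assuming every week is modelled.** Weeks 2–52 are 51 weeks, so 36/51 = 70.6%.

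**Late Week 16 visits, assuming daily entries run through the visit day.** Week 17 is Days 113–119 and reaches 4 daily entries if the visit is on about Day 116 or later. For such a patient the share is 35/51 = 68.6%. Week 18 is Days 120–126 and would need a visit on Day 123 or later. Later weeks would need still longer delays.

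**If the four-entry sentence does not cover NRS.** It refers to a component score, which could mean the diary only. NRS after Week 16 is then still defined as a mean of seven daily scores that do not exist, and no alternative is given. The value is undefined rather than missing.

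**With the single weekly score after Week 16.** All 36 weeks, and all 10 later windows, can have a value for a patient who completes the diary.

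**The case against.** The strongest reply is that the SAP contains a fallback. The patient-reported outcome row of Table 2-2 names e-diary data and says "The measurement closest to the scheduled day will be used". SAP 2.5.1.1 also refers to programming specifications for further visit-window detail. An analyst would probably use the weekly score, so actual loss of data is unlikely. That is fair as a forecast, but it does not resolve the text. SAP 2.5.1.2 applies its post-baseline selection rules only where nothing else is specified, and 2.5.1.1 does specify a rule for NRS. Table 2-2 also has no switch at Week 16: applied to NRS generally, it would displace the seven-day mean before Week 16 as well. Nothing in the SAP says that the programming specifications override 2.5.1.1.

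A second reply is that averaging the available scores in a week with one entry simply returns that entry. This is strained, because the rule names seven daily scores and the protocol attaches the four-entry minimum to NRS.

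Three narrower points have some force. The protocol gives no NRS derivation after Week 16, so the SAP may be filling a gap rather than changing a protocol analysis; the silence of Section 4 is then a side issue, and the conclusion does not depend on it. Table 2-1 is written for measurements taken at visits, so using it as the denominator for a diary item is an assumption. Finally, everything affected is exploratory and the scores can still be recovered, which limits the seriousness.

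**Conclusion.** The concern holds. As written, SAP 2.5.1.1 conflicts with the collection schedule and leaves NRS and NRS30 after Week 16 missing or undefined. The 62.5% figure assumes that the four-entry minimum covers NRS, that the Table 2-1 windows apply, and that the Week 16 visit is not very late. If every week is modelled instead, the share is 70.6%, or 68.6% for a patient whose late visit fills Week 17. If the minimum does not cover NRS, the same windows have no defined value.

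The effect is confined to exploratory outputs after Week 16: NRS30 rates, figures and the mixed model, per study and pooled, and the summary of worst skin pain on its original scale. The Week 16 NRS30 test uses daily data and belongs to the separate Week 16 SAP. This should be fixed, but it does not threaten the trial's main conclusions.

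**What to change.** In SAP 2.5.1.1, limit the seven-day mean and the four-entry minimum for pain NRS to Baseline and Weeks 1–16, as in Protocol 12.5.1. State that after Week 16 the single weekly score is used and, if a window holds more than one entry, the one closest to the scheduled day, as in Table 2-2. This follows the treatment SAP 2.11 already gives the HS Symptom Diary.

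Add a footnote to the NRS and NRS30 over-time outputs saying that values change from a seven-day mean to a single score after Week 16. Readers need this because the change coincides with the switch of placebo patients to secukinumab, and because NRS30 will then compare a single score with a seven-day-mean baseline.

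The cost is SAP wording, one derivation rule and one footnote. No new data are needed and the model does not change.
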